All participants who enroll in the study receive additional interactions with members of study staff, which may benefit participants by providing them with enhanced symptom monitoring while attending the partial hospital program. If participants show evidence of worsening symptoms, members of study staff are trained to immediately refer that person to their clinical team, which may enhance their existing clinical care. Finally, participants who are enrolled in the TAU+training condition receive access to an experimental cognitive training program that might help to reduce impulsivity.

Although this study also involves the risk of fatigue, frustration, and possible emotional distress while filling out questionnaires, these risk factors are common in studies of cognitive training in clinical samples. Previous studies using similar designs have yielded important conclusions about the utility of cognitive training paradigms among people with mental illness, while also carrying similar risks. We believe that the potential benefit of testing cognitive training in this setting outweighs the slight to moderate risks associated with this type of study design. Similarly, although the risk of breach of confidentiality is a significant concern for all research, we believe that the protections described above are adequate and that the benefit of novel treatment development is an important goal that partially offsets these risks. The proposed research also has broader potential benefits outside of the immediate study participants. The results of this study may well provide important conclusions about the extent to which cognitive training paradigms for impulsivity can be integrated into the partial hospital context, which may benefit future generations of partial hospital patients who struggle with similar forms of impulsivity.

MONITORING AND QUALITY ASSURANCE

The proposed research plan will strictly adhere to the data and safety monitoring guidelines set forth by McLean Hospital and Partners Healthcare. As the proposed study is a relatively small clinical trial that does not meet the definition of an NIH-defined Phase III clinical trial, and given the relatively low risk to study participants, we have not proposed a full Data Safety and Monitoring Board for the present study. However, we will implement a series of data and safety monitoring procedures to ensure optimal safety for all participants. The Principal Investigator ([name]) and the study sponsor ([name]) will hold responsibility for monitoring the safety of study participants and the security of data collected in this study.

Safety monitoring will be conducted on an ongoing basis via several procedures. First, participants' self-report measures include data that indexes patient safety (i.e., suicidal ideation, self-harm urges), and these measures will be reviewed daily by a member of study staff. If participants report an increase in risk based on these measures, the study staff member will immediately contact the PI. Also, members of study staff will inform the PI of any participants who verbally report any new safety concerns (either during the clinical interview or during routine study procedures). Any adverse events or serious adverse events will be reported to the Partners Healthcare Institutional Review Board (IRB). In accordance with Partners Healthcare policy, any unanticipated problems or adverse events will be reported within 5 working days or 7 calendar days from the date the problem is discovered. Serious adverse events would be reported within 24 hours of discovery.

In addition to these ongoing safety procedures, the PI will conduct a review of specific data points relevant to patient safety every twelve months. This review will encompass a statistical test of changes in symptoms on self-report measures from baseline to discharge in both

the TAU and the TAU+training groups. This will allow for evaluation of any potential negative effects arising from participation in the training program.

REFERENCES

1. Johnson, S. L., Tharp, J. A., Peckham, A.D., Sanchez, A.H., & Carver, C.S. (2016). Positive Urgency is related to difficulty inhibiting prepotent responses. *Emotion*, 16: 750-759.

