Design overview. We will conduct a randomized controlled trial of computerized cognitive control training among patients admitted to the BHP who report elevated scores on the urgency scales. Prior to beginning the randomized phase, we will enroll up to 20 participants into a pilot phase that will include the training program and all measure described below, with the exception of the EEG task. Next, Up to 90 patients will be randomized, with the goal of at least 68 patients completing baseline and discharge measures of impulsivity, symptoms, and craving for substances; half of these participants will be randomized to active training while half will undergo treatment as usual in the BHP. Participants randomized to the active training condition will be asked to complete eight to ten sessions of computerized cognitive training that combines working memory training and response inhibition training. This is a sub-study under the existing protocol entitled "Establishing the Effectiveness of Cognitive-Behavioral Partial Hospitalization for Anxiety, Depression, and Overall Functioning" (# 2010-P-001047/6). Data obtained under the existing BHP protocol will be shared with Investigators from this study.

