Power analysis: A priori power analysis conducted in G*Power indicated that a sample size of 68 individuals is necessary to achieve adequate power ($1 - \beta = 0.9$) to detect small to medium effects (Cohen's $f = 0.2$) in repeated-measures ANOVA. To ensure adequate power, we will recruit up to 90 patients to begin the study, based on predicted attrition rates (see "Potential Problems and Alternate Strategies"). To complete recruitment within two years, we will enroll 3.75 patients per month, or roughly one per week. In previous cognitive training studies conducted by [name] in the BHP, she has successfully enrolled patients at a rate of one per week, indicating that the target in the present study is highly feasible.

RISKS AND DISCOMFORTS

Potential Risks

i. **Privacy and Confidentiality of Data:** As with all research, there is a risk of loss of confidentiality and/or breach of data security. Given the substantial measures put in place to protect privacy and confidentiality within the BHP's clinical research program (described

above), there is a low likelihood of this risk.

ii. Frustration: The behavioral tasks that are administered at the baseline, training sessions, and discharge session require sustained concentration and focus. These tasks are relatively demanding by design, and thus some participants may feel moderately frustrated by the challenging nature of the tasks. However, in order to appropriately engage the putative underlying mechanisms of response inhibition and working memory capacity, it is necessary to include tasks that assess participants' ability to effectively recruit these domains under somewhat challenging conditions. Thus, there is a moderate possibility of frustration after completion of these tasks for some individuals.

iii. Fatigue: Participants may become tired following completion of relatively demanding cognitive tasks that require sustained concentration and focus. This may be particularly true for participants randomized to the TAU+training condition, as this condition involves up to 10 sessions of 15-minute cognitive exercises. It is likely that some participants may feel mentally fatigued after completion of such training sessions.

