**Date: 2/19/2021**

**NCT#: NCT03527550**

The statistical analysis plan for primary outcome measures is as follows:

1. Change in Average Score on Negative Urgency Scale:

*A 2 (condition: TAU, TAU + cognitive training) x 2 (time) repeated-measures Analysis of Variance (ANOVA) will be used to test change in negative urgency at time 1 (admission) and time 2 (discharge), and whether participants differ in their average change in negative urgency as a function of condition (interaction of condition X time).*

2. Change in Average Score on Positive Urgency Scale:

*A 2 (condition: TAU, TAU + cognitive training) x 2 (time) repeated-measures Analysis of Variance (ANOVA) will be used to test change in positive urgency at time 1 (admission) and time 2 (discharge), and whether participants differ in their average change in positive urgency as a function of condition (interaction of condition X time).*

Statistical Analysis Plan for Secondary Outcome Measures:

1. Change in Estimated Stop-Signal Reaction Time (SSRT) on Stop-Signal Task (ms):

*A 2 (condition: TAU, TAU + cognitive training) x 2 (time) repeated-measures Analysis of Variance (ANOVA) will be used to test change in SSRT at time 1 (admission) and time 2 (discharge), and whether participants differ in their average change in SSRT as a function of condition (interaction of condition X time).*

2. Feasibility of assessing change in event-related potentials (ERPs) during a Stop-Signal Task in a partial hospital population:

*This will be tested using descriptive statistics assessing the percentage of participants who are able to complete and provide ERP data for the stop-signal task.*

3. Completion Rates:

*This will be tested using descriptive statistics assessing the percentage of enrolled participants who complete the training intervention and the discharge session. This will be compared to an a priori benchmark of a 75% completion rate, based on previous studies.*

4. Average Perceived Helpfulness of Training

*This will be tested using descriptive statistics assessing the average rating of overall perceived helpfulness of the intervention, as rated by participants using a self-report form at the discharge session. This average rating will be compared to an a priori benchmark of an average rating of 4.0 or greater for each of the two training tasks (PASAT and Go/NoGo).*

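### The plan allows up to 24% loss, its primary ANOVA drops patients without a discharge score, and nothing requires urgency scores after training stops, so unequal loss can bias the effect

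*Protocol*

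**What the plan says.** The Power analysis paragraph states that "a sample size of 68 individuals is necessary to achieve adequate power", and then that "we will recruit up to 90 patients to begin the study, based on predicted attrition rates". The Design overview makes clear what those 68 must have: the enrolment target is set "with the goal of at least 68 patients completing baseline and discharge measures of impulsivity, symptoms, and craving for substances". Allocation is one half to each arm.

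For the first primary outcome, the SAP says that a 2 x 2 repeated-measures ANOVA "will be used to test change in negative urgency at time 1 (admission) and time 2 (discharge", with the condition x time interaction as the treatment comparison. Positive urgency is handled in the same way. The protocol's Biostatistical Analysis section gives the same 2 x 2 layout.

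On tolerability, the Fatigue paragraph under Risks and Discomforts says of tiredness after the tasks: "This may be particularly true for participants randomized to the TAU+training condition, as this condition involves up to 10 sessions of 15-minute cognitive exercises".

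Neither document names an analysis set, an intention-to-treat principle, a missing-data method or a sensitivity analysis. Neither says whether a patient who stops training still completes the urgency scales at discharge. For attrition, the Power analysis refers to a section called *Potential Problems and Alternate Strategies*, which is not in the text available to us.

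**The concern.** With two time points, the condition x time test in a classical repeated-measures ANOVA is the same as a two-sample t-test on the change scores. A patient without a discharge score has no change score and contributes nothing. The documents state no complete-case rule, but the method imposes one.

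Randomisation protects the comparison of everyone assigned. It does not protect the comparison of those who happen to have a discharge score. Only TAU+CCT contains up to ten additional demanding sessions, and the protocol itself expects more fatigue there, so loss that differs between arms is plausible. If the patients lost also change differently from those who stay, the interaction no longer estimates the effect of adding training in the randomised groups. The direction of the error depends on who leaves.

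**Working it through.** **1. The plan's own figure.** Inputs from the Power analysis: f = 0.2, power 0.90, N = 68. Not stated, so assumed: alpha 0.05 and a baseline-discharge correlation of 0.5. For the within-between interaction with m = 2 time points:

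lambda = f² x N x m / (1 - rho) = 0.04 x 68 x 2 / 0.5 = 10.88, with 1 and 66 degrees of freedom.

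Power is 0.9015, so 68 reproduces. The result depends on the assumed correlation: 0.3 would need 94 patients and 0.7 would need 42.

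**2. The design effect on the scale of change.** With 34 per arm, the squared noncentrality of the t-test is d² x 34/2. Setting 17 d² = 10.88 gives d = 0.8 SD of change. At correlation 0.5, one SD of change equals one SD of the score, since sqrt(2 x (1 - 0.5)) = 1.

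**3. Allowed loss.** 1 - 68/90 = 22/90 = 24.4%. This is a ceiling, because the text says up to 90 and at least 68.

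**4. Bias by formula.** Let the gap be how much better, in SD of change, the patients with a discharge score do than the patients lost. Then

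bias = loss(CCT) x gap(CCT) - loss(TAU) x gap(TAU).

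The documents give neither the gaps nor the split of losses. Taking 45 per arm, 22 lost and gaps of 0.25 to 1.0 SD:

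| Lost, CCT v TAU | Gap | Bias (SD) | Type I error at gap 0.5 |
|---|---|---|---|
| 11 v 11 | equal | 0 | 5.0% |
| 11 v 11 | CCT only | 0.06 to 0.24 | 8.0% |
| 16 v 6 | equal | 0.06 to 0.22 | 7.4% |
| 22 v 0 | CCT only | 0.12 to 0.49 | 15.9% |

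Example, third row at gap 0.5: (16/45 - 6/45) x 0.5 = 0.111 SD. The standard error is sqrt(1/29 + 1/39) = 0.245, so the shift is 0.45 standard errors and the two-sided rejection rate is 7.4%. Power for the design effect stays at 88% to 91% in these splits, so the issue is bias and not power.

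**5. Simulation.** 45 per arm, correlation 0.5, no true effect, logistic drop-out. Slopes are log-odds per SD, and all loss rates and slopes are assumptions.

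| Loss, CCT / TAU | Mechanism | Change-score test | Baseline-adjusted |
|---|---|---|---|
| 24.4% / 24.4% | change, slope 1, both arms | 0.00, 5% | not needed |
| 30% / 19% | change, slope 1, both arms | 0.09 SD, 7% | not shown |
| 36% / 12% | change, slope 0.3 in CCT, random in TAU | 0.11 SD, 7% | not shown |
| 36% / 12% | change, slope 1 in CCT, random in TAU | 0.30 SD, 23% | 0.23 SD, 18% to 20% |
| 36% / 12% | baseline, slope 1 in CCT, random in TAU | 0.15 SD the other way, 9% | 0.00, 5% |

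Where patients with less improvement leave, the error is a spurious benefit of training. Where patients with high baseline urgency leave, it works against training. Conditioning on baseline removes the second error and only part of the first.

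**6. If no scores were lost.** With 90 analysed, lambda = 0.04 x 90 x 2 / 0.5 = 14.4 and power is 96.4%.

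**The case against.** Several stronger readings are tempting, and the documents do not support them.

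- *The analysis compares trained completers with TAU.* The 68 are patients who complete measures, not training. The Cognitive Control Training section accepts as few as five sessions for scheduling reasons, and the analysis section considers the percentage of sessions completed as a covariate. A partly trained patient with a discharge score is therefore analysed.
- *A patient who quits training has no second visit.* One section is titled post-training assessment, but the SAP fixes time 2 as discharge for both arms.
- *Nothing keeps these patients in follow-up.* The parent protocol asks every program patient for self-report at discharge and at four and eight weeks, and those data serve as outcome assessments here. This weakens the point but does not close it. The measures named as routine care are the MINI and PHQ-9, and the urgency scales are listed separately as research measures. Whether they are in the parent protocol's discharge set is an open question.
- *The pilot effect of d = 0.66 can be scaled down by the share lost.* That figure is a pre-post change in a non-clinical sample, not a difference between arms.

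Two further objections carry weight. First, unequal loss alone does not cause bias: the patients lost must also differ in change. The largest simulated figures above need a steep mechanism in one arm, under which lost CCT patients do about 0.83 SD worse than those retained, roughly the whole design effect. Second, the attrition section that the protocol cites may contain relevant provisions that we cannot see. The later SAP has none in its primary-outcome text.

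The protocol's term mixed-model ANOVA could also be read as a likelihood-based model that keeps patients with baseline only. The 2 x 2 layout, the power calculation and the SAP's wording all point to the classical analysis.

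**Conclusion.** The concern holds in this form: the plan permits up to 24.4% loss, uses a test that drops patients without a discharge score, and neither requires discharge urgency after training stops nor defines an analysis of all randomised patients. Unequal, outcome-related loss can therefore bias the condition x time effect. It cannot be said that it will.

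Across the simulated scenarios tabulated above, the bias runs from 0 to about 0.3 SD, with type I error from 5% to about 23%. Harsher assumptions go further: all 22 losses in one arm with a 1 SD gap gives 0.49 SD, and a slope of 1.5 in the 36% / 12% case gives 0.39 SD and 38%. Milder ones give about 0.1 SD. All of these rest on assumed loss rates, mechanisms and a correlation of 0.5, none of which the documents supply. The absence of the safeguards is read from the available text, subject to the attrition section that we do not have.

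**What to change.** 1. **Protocol.** State that stopping training is not withdrawal from assessment, and that every randomised patient still in the program completes both urgency scales at discharge, in both arms, whatever the number of sessions done. This matters most, because no model fully repairs loss that depends on change. Preliminary Study A had discharge-day urgency scores from program patients, so collection is feasible.
2. **SAP, primary outcomes.** Analyse all randomised patients with any urgency score, by assigned arm. Replace the change-score ANOVA with a likelihood-based mixed model that conditions on baseline (common baseline mean, condition x time). This deals with baseline-related loss but only part of change-related loss, and with two time points the patients with baseline only add little information.
3. **SAP, missing data.** Add multiple imputation using the PHQ-9 and other self-report scores already collected, with a missing-not-at-random (delta) sensitivity analysis. Report loss and reasons by arm.

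The cost is one protocol paragraph, some SAP wording and analysis, and a few minutes of questionnaires for patients who stop training but are still on site. The estimate may be smaller than the one from patients with both scores.

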
SPECIFIC AIMS

1. The first aim of this study is to confirm target engagement of cognitive control training at both the behavioral and neural levels of analysis in a clinical sample of patients reporting high levels of urgency. We predict that compared to the control group, patients completing cognitive training will show lower interference (improved behavioral performance) and decreased ERN and N2 amplitudes on a Stop-Signal response inhibition task.
2. The second aim is to examine clinical outcomes of cognitive control training. Based on Preliminary Study A, we predict that all patients receiving treatment at the BHP will report lower urgency scores at discharge; however, we predict that this decrease will be significantly greater in those receiving cognitive training. In addition, we predict that

participation in the training will be associated with greater reductions in depression symptoms, urges to engage in NSSI, and craving related to substance use.

3. The third aim is to assess this training's feasibility and acceptability to patients in a real-world clinical setting. We predict that at least 75% of enrolled patients will complete all training sessions.

SUBJECT SELECTION

This is a sub-study under the existing protocol entitled "Establishing the Effectiveness of Cognitive-Behavioral Partial Hospitalization for Anxiety, Depression, and Overall Functioning" (# 2010-P-001047/6). We will recruit 110 participants from the patient population at the McLean Hospital Behavioral Health Partial Hospital Program (BHP). Inclusion criteria include: (a) BHP patient, (b) score above a 3 on either the UPPS Negative Urgency Scale or the UPPS Positive Urgency Scale at admission, (c) able to complete a computer task for 15 minutes, and (d) consent to main BHP study protocol (# 2010-P-001047). Participants will be excluded from participation if they are experiencing acute symptoms of mania or psychosis; if they are currently undergoing ECT; or if they have a history of a traumatic brain injury. Participants who are left-handed will be excluded from the EEG portion of the study but will be allowed to complete all other portions of the study.

Additional inclusion criteria for the research study will be consistent with admission criteria for the BHP program. Specifically, patients who are acutely psychotic and are deemed unfit for admission at the BHP will not be invited to participate in this study.

SUBJECT ENROLLMENT

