Participants randomized to complete the cognitive control training exercises will complete 8 to 10 sessions of the exercises described below, lasting about 15 minutes each time. Prior to each training session, participants will view a brief powerpoint slide reminding them how the task pertains to impulsivity. Participants will be asked to complete ten sessions; however, participants may complete as few as five sessions if there are problems finding time to schedule all ten sessions (e.g., computer availability, participant availability during lunchtime or before or after program hours, etc.). The two training tasks will alternate on each day of training: each day of training, participants will complete either the Go/NoGo task or the PASAT task described below; participants will be randomly assigned to begin with either the Go/NoGo task or the PASAT task.

a. *Adaptive Go/NoGo* is a response inhibition training paradigm previously used by this PI to train inhibition (19) based on similar Go/NoGo training paradigms used in previous training studies (i.e., 48, 68). Participants are instructed to press a button as fast as possible (“go”) whenever they see a stimulus (a single letter) presented onscreen; however, on each new block they must withhold their response when a target letter is presented (“no-go”), with the target letter switching in each new block. The training includes three 5-minute blocks per session. Similar to other inhibition training paradigms (46), the difficulty level is adapted to performance

based on participants' reaction time to "go" trials; as participants correctly respond to "go" trials, the amount of time in which they have to respond to these trials is reduced. The nonadaptive version of this task will be used to assess baseline and post-training task performance.

b. *Adaptive Paced Auditory Serial Addition Task (PASAT, [51])* In this task, participants listen to a series of aurally-presented numbers and are instructed to add each number to the last number presented and enter the sum onscreen. The performance-adaptive version of the task decreases the inter-stimulus interval as performance improves (making the task more challenging by reducing the amount of time per trial, or decreasing difficulty by increasing time). The training includes three 5-minute blocks per session. The nonadaptive version of this task will be used to assess baseline and post-training task performance.

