Sessions will be completed during the lunch hour, in between groups, or at the end of the day. Sessions will begin on the second or third day and continue until discharge. The average length of stay in the BHPP is 8.5 days. Sessions will be completed in the BHP computer lab, where patients complete daily progress monitoring as part of their standard clinical care, or a private room when available. A member of the study staff, typically the research coordinator, will set up the computer task and be available for any questions or problems.

BIOSTATISTICAL ANALYSIS: ERP data will be pre-processed to remove artifacts (e.g., by using independent component analyses) and identify ERPs using BrainVision Analyzer. Hypothesis 1 will be tested using a 2 (condition: TAU+training, TAU) x 2 (time: baseline, discharge) mixed-model analysis of variance (ANOVA) with Stop-Signal Reaction Time as the dependent variable; two separate ANOVAs with the same predictors will also test dependent variables of ERN and N2 amplitudes. Hypothesis 2-3 will be similarly tested via mixed-model ANOVA with the same predictors; one model will test the DV of Negative Urgency; one will test the model of Positive Urgency; and three models will test change in craving, depression, and self-harm urges. Hypothesis 4 will be tested via descriptive statistics assessing the percentage of enrolled participants who complete the training intervention and their mean level of satisfaction at discharge. Analyses will consider the impact of several a priori potential confounds on effects of the intervention, using Pearson correlations to test if performance on cognitive tasks are related to age, medication, primary diagnosis, or percentage of completed training sessions. If significant correlations are identified, these variables will be included in the above analyses as covariates.

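### The protocol's covariate rule can put percentage of completed training sessions, which arises after randomisation and only in TAU+CCT, into the condition × time models, and the SAP does not withdraw it

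*Protocol*

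**What the plan says.** The Biostatistical Analysis section of the protocol describes condition × time mixed-model ANOVAs for SSRT and both urgency scales. For the ERPs, "two separate ANOVAs with the same predictors will also test dependent variables of ERN and N2 amplitudes"; for symptoms, "three models will test change in craving, depression, and self-harm urges". It then names several possible confounders in advance and screens them by "using Pearson correlations to test if performance on cognitive tasks are related to age, medication, primary diagnosis, or percentage of completed training sessions". The consequence is stated: "If significant correlations are identified, these variables will be included in the above analyses as covariates". Nothing limits the session variable to one arm or to a secondary analysis.

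Only one arm trains, and the comparator is treatment as usual without sham training. The Design overview says "Participants randomized to the active training condition will be asked to complete eight to ten sessions of computerized cognitive training". Under Cognitive Control Training, "participants may complete as few as five sessions if there are problems finding time to schedule all ten sessions", and "Sessions will begin on the second or third day and continue until discharge". Aim 3 adds: "We predict that at least 75% of enrolled patients will complete all training sessions".

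The SAP, dated after the protocol, gives 2 × 2 repeated-measures ANOVAs for Negative Urgency, Positive Urgency and SSRT with no covariates. For ERPs it lists only a descriptive feasibility outcome. It gives no model for craving, depression or self-harm urges, and it neither repeats nor withdraws the covariate rule.

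**The concern.** A confounder of a randomised comparison must precede assignment. Session completion follows assignment and is the amount of treatment received, so conditioning on it changes the question from the effect of being assigned to training to something else.

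The rule also leaves four things open: how TAU participants are coded, which task score and time point the correlation uses, whether arms are pooled, and whether a covariate × time term is fitted. Depending on these choices, the adjusted analysis is unaffected, seriously damaged or impossible to fit, and the choice can be made after the data are seen.

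A link between session count and outcome is plausible without any training effect. Sessions run until discharge, so the count partly reflects length of stay.

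**Working it through.** **Inputs from the documents.** N = 68, equal allocation (34 per arm), power 0.90, f = 0.2 (Power analysis); 8 to 10 sessions, as few as five allowed; 75% predicted to complete all sessions.

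**Assumptions.** Two-sided alpha 0.05; baseline–discharge correlation ρ = 0.5; unit SD at each time, so the change score has SD √(2(1 − 0.5)) = 1. Three session patterns for TAU+CCT: uniform on 5–10; uniform on 8–10; and 75% completing ten with the rest uniform on 0–9.

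**1. The plan's own figure.** λ = f² × N × 2/(1 − ρ) = 0.04 × 68 × 2/0.5 = 10.88 on 1 and 66 df gives power 0.90, so the stated sample size reproduces. The matching difference in change is √(10.88 × 4/68) = 0.80 SD. The unadjusted SE is √(2/34) = 0.24.

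**2. Adjusted, session count unrelated to benefit or outcome.** Code TAU as 0% and fit covariate × time, which is the same as regressing change on arm and sessions. With mean m and SD s of sessions in TAU+CCT, the squared correlation of sessions with arm is (m²/4)/(m²/4 + s²/2). Hence VIF = 1 + m²/(2s²), and λ is divided by VIF (65 error df). Results from 5,000 simulated trials per scenario are in brackets.

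| Sessions | m | s | VIF | Adjusted SE | Power |
|---|---|---|---|---|---|
| 5–10 | 7.5 | 1.71 | 10.6 (10.9) | 0.79 (0.80) | 0.17 (0.16) |
| 8–10 | 9.0 | 0.82 | 61.8 (63) | 1.91 (1.92) | 0.07 (0.07) |
| 75% complete ten | 8.625 | 2.78 | 5.8 (6.0) | 0.58 (0.59) | 0.27 (0.28) |

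Repeat simulations of the last row gave 0.25 to 0.28. At ρ = 0.3, power falls from 0.78 to 0.14 (5–10) and from 0.79 to 0.20 (75% pattern). At ρ = 0.7, it falls from 0.99 to 0.26 and 0.40.

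**3. Benefit proportional to sessions.** The covariate carries the whole effect. The adjusted arm effect is about 0 and the rejection rate about 0.05 in all three patterns.

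**4. Session count otherwise prognostic.** If sessions correlate r with change within TAU+CCT, the adjusted effect is 0.8 − r × m/s.
- 5–10: m/s = 4.39. At r = 0.2 this gives 0.8 − 0.88 = −0.08 (simulated −0.06); at r = −0.2, 1.68 (1.69).
- 75% pattern: m/s = 3.10. At r = 0.2 this gives 0.8 − 0.62 = 0.18 (0.16); at r = −0.2, 1.42 (1.43).
- With no true effect and r = 0.2, the adjusted test rejects in 19% (5–10) or 17% (75% pattern) of simulated trials, against about 5% unadjusted.

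**5. How often the rule fires, one task.**

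| Screen | Task effect 0 | 0.3 SD | 0.5 SD | 0.8 SD |
|---|---|---|---|---|
| Change score, arms pooled, TAU = 0%, 5–10 | 5% | 21% | 49% | 87% |
| Same, 75% pattern | 5% | 20% | 46% | 83% |

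Within TAU+CCT only, it fires in about 5% of trials if the task gain does not depend on sessions. If the gain is proportional to sessions at 0.8 SD, it fires in up to 17% (5–10) or 30% (75% pattern). With a baseline task score the rate is about 5%.

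**6. Other ways of fitting it.** A main effect alone is constant over time, cancels from the change score and leaves condition × time unchanged. If TAU is coded missing, complete-case fitting removes the TAU arm and the contrast cannot be estimated.

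**The case against.** The strongest reply concerns reach and probability. The later SAP gives complete, covariate-free models for both primary outcomes and SSRT, and these can be read as replacing the rule there. The SAP reduces ERPs to descriptive feasibility and does not list craving, depression or self-harm urges, so the remaining exposure may lie outside its inferential outcomes. The large power losses need a significant screen, TAU coded 0% and covariate × time together. A percentage of sessions is not naturally defined for TAU, so a screen within TAU+CCT is at least as natural as a pooled one. If the rule fired in 5% of trials, independently of the outcome, overall power would be about 0.95 × 0.90 + 0.05 × 0.16 = 0.86. The 0–9 session tail and the correlations of ±0.2 are assumed, and the proportional-benefit result follows almost by definition.

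All of this stands as a limit on how often harm occurs. It does not rescue the rule. The SAP does not say that it replaces the protocol paragraph or that the protocol's ERP and symptom models are dropped. No reading makes session completion a valid adjustment for the randomised effect. The one-task firing rates may also be low, since several tasks are administered. On the pooled change-score reading, the task improvement predicted in Aim 1 is itself what triggers inclusion.

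**Conclusion.** The concern holds and should be fixed, though it does not invalidate the trial. The protocol states a rule that can admit a post-randomisation, single-arm variable into the between-arm models. The SAP's analysis text leaves its status unclear for Negative Urgency, Positive Urgency and SSRT, and does not address it for ERN, N2, craving, depression and self-harm urges.

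The figures above are conditional on the rule firing and on the damaging way of fitting it. In that case the test loses most of its power, and its estimate can be driven to zero or biased in either direction. They also rest on 34 per arm, the assumed alpha and ρ, and the assumed session patterns. ERN and N2 exclude left-handed participants, so their numbers would be smaller by an amount the documents do not give.

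**What to change.** In the protocol's Biostatistical Analysis section, remove session completion from the list of candidate covariates. Add one sentence to the SAP: percentage of completed training sessions enters no between-arm model (Negative Urgency, Positive Urgency, SSRT, ERN, N2, craving, depression, self-harm urges) and is used only in a labelled exploratory dose-response analysis within TAU+CCT.

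This costs one deleted phrase and one added sentence, with no new data, participants or model type. The dose-response question is kept. How age, medication and primary diagnosis are handled is a separate matter.
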